11.3 Primary Endpoint Estimand

The primary efficacy endpoint is the absolute change in MADRS total scores from Baseline to end of Treatment visit at Week 6 in subjects on ADT plus Lumateperone or matching placebo.

The main estimand for the primary efficacy endpoint is defined as follows:

- Target population(TP):Total Population: All randomized participants with MDD and history of early life abuse (Baseline MADRS score ≥ 22) as defined by the study inclusion/exclusion criteria who are randomized and dosed

- Variable: Change from Baseline to Week 6 in the MADRS total scores (Visit 7)

Intercurrent events (ICE)

1. Study or treatment discontinuation

- a. Due to lack of efficacy

- b. Due to adverse event related to study medication

- c. Due to adverse event unrelated to study medication

- d. Due to other reasons

2. Treatment with prohibited medication

3. Death

- a. Related to MDD

- b. Unrelated to MDD

- ICE strategy

- o ICE 1a, 1b, 2: A hypothetical strategy will be applied assuming that patients after the ICE follow the course of patients receiving placebo.

- o ICE 1c, 1d, 3b: A hypothetical strategy will be applied assuming that patients after the ICE follow the course of the arm they were randomized to.

- o ICE 3a: A composite strategy will be applied by imputing values after the ICE with the worst possible MADRS score (=60).

10.2 Secondary Endpoint Estimand: The key secondary efficacy endpoint is the change from baseline to end of Week 6 in the CGI-S score.

11.4 Efficacy Estimand Analysis

Main estimands are defined for the primary efficacy variable:

- Absolute change from Baseline to Week 6 of the MADRS total score

and for the following 3 key secondary efficacy variables in hierarchical rank order of the hypothesis testing procedure:

- MADRS response rate (proportion of subjects with an improvement $\geq 50\%$ in the Baseline MADRS total score) at End of Treatment (EOT) Week 6, Lumateperone as compared to placebo

- MADRS remission rate (proportion of subjects with a MADRS total score ≤ 10) EOT Week 6, Lumateperone as compared to placebo

- Change from Baseline to EOT Week -6 in the Clinical Global Impression of Severity (CGI-S) score, Lumateperone as compared to placebo

Confirmatory testing will be performed only for these main estimands, whereby the testing of the key secondary estimands will follow the ordered hierarchical approach.

The primary statistical analysis of all confirmatory tested estimands will be performed on the Total Population, using the mixed-effect model repeated measure (MMRM) analysis. For the main primary estimand, the changes from baseline in MADRS total score will be analyzed using a Mixed Model with

Repeated Measures (MMRM). This model will include Treatment, Visit, Treatment-by-Visit interaction and the number of failed prior treatments (1 or more than 1) as fixed effects, Baseline value as a covariate, and Visit as the repeated effect. The estimated means for each arm as well as the estimated treatment effect (Lumateperone – Placebo) along with the 95% confidence intervals for the treatment effect will be presented for each visit. The primary estimand will be estimated as the difference between treatment means (MMRM least-squares) at the EOT Week 6 (Visit 7).

As a sensitivity analysis for all estimands, the MMRM analysis will be performed using a range of missing value imputations. For the main estimand of the primary efficacy, a tipping point analysis will be applied to investigate the robustness of the analysis results.

Study Elements Requiring Additional Information or Approvals

9. Public Registration and Reporting Requirements

Federal regulations, policy, and some journal guidelines require public registration and results reporting for studies that meet the definition of a clinical trial.

Note that the various definitions of “clinical trial” subject to these requirements can be quite broad and include things like behavioral interventions conducted outside of traditional healthcare settings.

Answer the following questions and review the linked guidance to see if any of these requirements apply to this study.

9a. Does this study involve prospectively assigning participants, or groups of participants, to one or more research intervention(s)?

Intervention includes both physical procedures by which data/specimens are gathered and manipulation of the participant or the participant’s environment for research purposes. Can include control groups.

- No → *Skip to item 10*
- Yes

9b. Is the intention of the study to evaluate the effect of a research intervention on *health-related biomedical or behavioral outcomes*?

- No → *Skip to item 10*
- Yes

9c. If yes to the above, go to [UT Guidance on Clinical Trials Registration and Results Reporting](#) and review requirements that may be applicable and select which of the following apply to this study:

- Intended to be submitted for publication in a journal subject to International Committee of Medical Journal Editors (ICMJE) requirements
- NIH-funded Clinical Trial (*be sure list funding on the Study Funding section of the UTRMS application*)
- FDA-defined Applicable Clinical Trial
- Intended to have routine clinical trial costs covered by the Center for Medicare and Medicaid Services (CMS)
- Registration is required per the terms of the award/funding agency
- Meets none of the above requirements but will register voluntarily
- None of the above

9d. Will the UT Austin study team register this study on ClinicalTrials.gov?

[Click here](#) for information on how to identify the “Responsible Party” for registration.

- Yes
- No – This is a multi-site study and the UT PI is not the Responsible Party for registration. The external Responsible Party is aware of their duty to register the study.

- No – This study involves an IND or IDE held by someone other than the UT PI, the IND/IDE holder is the Responsible Party and is aware of their duty to register the study.
- No – This study meets none of the requirements in item 9c above and the study team prefers not to register

9e. Attest that all relevant reporting requirements for the study will be followed as applicable (regardless of ClinicalTrials.gov registration).

Use the linked guidance in item 9c and review the section titled “Reporting Results” for guidance. This box must be checked to confirm you have reviewed the requirements, even if you determine no reporting requirements apply to you.

- Confirm

10. Does the research involve biospecimens of any kind (e.g. blood, tissue, saliva, etc.), biohazards, recombinant DNA, or gene transfer?

- No → *Skip to item 11*

- Yes

10a. Does the research involve human embryonic, human induced pluripotent, or human totipotent stem cells; or human gametes or embryos?

- No

- Yes → *Be aware that additional review criteria may apply, see [UT IRB Policies & Procedures section 18](#) for guidance.*

10b. Will biospecimens be used and stored at UT?

- No, biospecimens collected will be stored at an external site that has responsibility for biosafety
- Yes → [UT Institutional Biosafety Committee \(IBC\) approval](#) is needed. Provide the UT IBC number in the text box below:

10c. Does the research involve prospective collection of blood from participants?

- No → *Skip to item 11*

- Yes

10d. Select all methods that will be used to collect blood samples:

Note that procedures for all forms of specimen collection should be described in the [Study Procedures](#) section above. The IRB requires the following specific details for blood collection to determine the appropriate review level.

- Research sample collected at the same time as non-research blood collection (i.e. extra blood collected)
- Individual needle stick(s)
- Indwelling catheter placed solely for this study
- Accessing indwelling catheter placed for non-research purposes
- Other, specify in text box below:

10e. Specify the timing and frequency of blood collection and the volume of blood obtained at each collection:

Blood will be collected four times during the study; the total amount of blood each draw is two tubes, 1 tube that is 9 mL of blood and another that is 8.5 mL. Reference the study procedures chart as well as the clinical assessments section for frequency.

11. Does the research involve genetic testing/analysis?

This may include research involving identification and location of specific genes, study of gene products, inherited human traits, or identification and analysis of DNA mutations.

No → [Skip to item 12](#)

Yes

11a. Describe the genetic testing/analysis involved in this study:

If this is already described earlier in the form (such in the Study Procedures or Data Analysis items), please reference the appropriate sections where this can be found in the box below.

11b. Are participants able to opt-out of or withdraw from the genetic testing part of the research while continuing with other parts of the research?

Be sure this response aligns with language included in the consent form(s).

Yes

No

11c. Will or might genetic testing/analysis reveal clinically relevant findings for participants?

For example, medical conditions that could be treated or information about paternity/lineage.

No → [Skip to item 12](#)

Yes → *Describe potential findings below:*

11d. Describe the procedures for providing clinically relevant genetic results to participants:

Include whether or not genetic counseling will be offered to participants. Specify whether or not participants will be offered the option to decline learning the results, or if any results will not be provided (and if so, why). Be sure this response aligns with language provided in the consent form(s).

11e. Will genetic tests be run in a [CLIA-certified](#) laboratory?

Yes

No → *If no, explain below why this is not necessary:*

12. For this study, will the researchers obtain, use, or disclose Protected Health Information (PHI) regulated under the Health Insurance Portability and Accountability Act (HIPAA)?

This typically applies to research involving access to medical records. This does not include self-reported health information disclosed as part of research surveys/interviews. Guidance on HIPAA protected PHI is available [here](#).

No → [Skip to item 13](#)

Yes

12a. Select all HIPAA-covered entities providing PHI:

 UT Health Austin	 Ascension Seton/other Ascension locations*
 UT Austin University Health Services	 Dell Children's Medical Center*
 CommUnity Care	 Central Health
 Other, specify:	Clinical Pathologies Laboratory, Biomedical Imaging Center

**For studies obtaining data from Ascension facilities, please submit a request to the [Seton Site Approval Tool \(SAT\)](#) and upload the confirmation email that states the request has been submitted in UTRMS under "Other Documents." Please note, we do NOT need the final approval letter (you will not receive SAT approval until after IRB approval is granted). If you encounter issues or have questions about SAT, please reach out to [contact].*

12b. List the data points or attach a list of the data to be collected about each subject from their medical records or other HIPAA protected data source(s). Select one of the following:

This list is uploaded to UTRMS on the Local Site Documents page under "Other Attachments"
 All data points listed in the text box below:

Medical History will be self-reported by the participant, as listed in the protocol. The following will be collected as participation in this study:

- Lab & Pathology Results
- MRI Imaging

12c. Select all pathways for obtaining HIPAA authorization for accessing PHI for this research:

NOTE: If obtaining authorization from Ascension patients, use of Ascension's stand-alone HIPAA authorization form is required and this form should be uploaded on the Local Site Documents page in UTRMS under "Other Attachments." Otherwise, non-Ascension HIPAA authorization may be combined with Informed Consent using the HIPAA template language embedded within the 920 Standard Consent Template. All UT Austin IRB templates are available in the Templates tab of the [UTRMS-IRB Library](#).

Obtaining HIPAA authorization from participants to access PHI → *Skip to item 13 if only this box is checked*
 Requesting *full* waiver of participant authorization
 Requesting *partial* waiver of authorization to access PHI for screening or recruitment only

All of the following must be checked to qualify for a partial waiver for screening or recruitment:

- Attest that PHI will be accessed ONLY to identify eligible subjects for recruitment in this research. Continued access to PHI will be limited to those who later volunteer for the study and provide written authorization.
- Attest that PHI will be accessed only by individuals who have authorization to access the records outside of the research context.
- Attest that researchers will not move or transmit identifiable PHI from the covered entity (i.e. the institution holding the records, such as the clinic).

12d. Complete the following if requesting a *full* or *partial* waiver of HIPAA authorization:

I. Specify the date range of records that will be accessed:

Start date (month/year):

End date (month/year):

II. Provide a justification for why the research could not practically be conducted without access to PHI and the waiver of patient authorization requested:

- Identification/recruitment:** – access to records is needed to identify eligible subjects (e.g., chart reviews, partial waiver for recruitment, etc.)
- Large number of subjects projected** – potential subject population includes a large number of records to review and it is not feasible to attempt contact with all subjects
- Outdated records** – This is a retrospective study involving subjects who may have moved or expired and researchers cannot feasibly attempt to contact required sample
- Total population required** - The nature of the research is such that findings will not be valid, or will be significantly skewed, if the total eligible population is not included.

Select all that apply above OR provide different justification below.

- None of the above; specify other justification:

Note that inconvenience or limited time/resources alone are not sufficient justifications for waiving a patient's right to authorize disclosure of their PHI.

III. **Attest that the protected health information will not be reused or disclosed to any other person or entity, except as required by law, for authorized oversight of the research study, or for other research where the use or disclosure of the PHI meets IRB and HIPAA requirements.**
This box must be checked.

- Confirm

IV. **The HIPAA regulation requires reasonable efforts to limit protected health information to the minimum necessary to accomplish the intended purpose of the use, disclosure or request. Review the linked guidance and attest below that you are obtaining only the minimum information necessary to complete the waived activities:**
This box must be checked.

- Confirm

V. **Provide any additional information you'd like the IRB to consider for why/how all the listed data points in item 12b are necessary to answer the research question and comply with the minimum necessary requirement described above (if none, this can be left blank):**

13. Does this study involve Deception and/or Incomplete Disclosure?

See [IRB Policies and Procedures Section 15](#) for a description of deception.

Deception (as applies to research) means intentionally giving research subjects false information in order to establish false beliefs during the course of a research study.

Incomplete disclosure means that the investigator withholds some information about the real purpose of the study or the nature of the research procedures.

No → **skip to item 14**

Yes → Note that an alteration of informed consent may need to be requested in the [Consent Pathways](#) section. Please address items below:

13a. Describe the nature of deception/incomplete disclosure and why it is necessary to conduct the research.

13b. Will participants be debriefed (i.e. provided additional pertinent information about the nature of the deception/incomplete disclosure) after research activities are completed?

Yes

No → provide a strong justification below for why this will not occur, then **skip to item 14**:

13c. Describe debriefing procedures.

NOTE: Upload the debriefing form to UTRMS-IRB in the “Local Site Documents” section.

13d. Will research participants have the opportunity to withdraw their data during/after debriefing?

Yes → Be sure to include language about this option in the uploaded debriefing script.

No → Provide a strong justification below for why this will not occur:

14. Research Activities Requiring Supplemental Forms or Additional Oversight

Select each of the items below that are relevant to your research. If none apply, this section can be left blank.
	
For each item selected, complete and upload the associated Supplemental Form in UTRMS-IRB under “Other Attachments” or review the linked guidance and follow instructions as applicable.

 Investigational Drugs, Biologics, Supplements, or other regulated non-device products	UT Supplement 906 – Investigational Drugs, Biologics, and Non-Devices
 Investigational Device	UT Supplement 905 - Investigational Device
 International Research This includes research conducted outside the US, direct remote interactions with international participants (i.e. Zoom interviews), and research that will collect identifiable data from international participants (including online surveys).	UT Supplement 908 - International Research
 Department of Defense (DoD) This includes all research involving DoD funding, facilities, data, or personnel (i.e. active military personnel are targeted/discriminable in the data collected). See Policies & Procedures section 25.1 for guidance on DoD applicability.	UT Supplement 911 - Department of Defense

 Energy introduced to the subject (electrical, magnetic, light)	For research involving these activities, be aware that the IRB may solicit ancillary review from the UT Austin Environmental Health & Safety (EHS) office . Any additional requirements may be communicated during review. Guidance on EHS policies and reviews is available here: IRB-ML101-Guidance for Institutional Reviews and Approvals of Human Research at UT Austin (PDF) .
 Radiation exposure without direct clinical benefit	
 Use of Artificial Intelligence (AI) in research	
As part of UT ISO's mission and with the growing use of AI in research, all research that involves use of AI should be in alignment with ISO's Acceptable Use of AI Policy.
 
If your AI platform use is not listed or in alignment with the policy above, contact UT ISO at [contact] prior to conducting any research with that AI tool. It is strongly recommended to confirm acceptability prior to submitting to the IRB.

Subject Population

15. Sample Size

Enter the maximum total anticipated sample size, including a breakdown of target sample size per participant group (if more than one). Note that the IRB is looking for the number of individual human subjects you plan to enroll.

50 Participants Total: 25 enrolled in a placebo group and 25 enrolled into the treatment group

Participants are those who have MDD and history of early life trauma.

Refer to inclusion/exclusion criteria for detailed list of criteria necessary to meet enrollment.

16. Sample size rationale

Describe your sample size rational below.

Sample size is chosen to have moderate statistical power and still ensure feasibility for study completion.

17. Research Participant Information

Describe the general characteristics of the subject populations or groups including gender, health status, and any other relevant characteristics. **If you have multiple research populations (e.g. teachers and students), clearly outline characteristics for each group.**

Male and Female inpatient, who have Major Depressive Disorder MDD and history of early life trauma who have an inadequate response to on-going SSRI treatment

18. Age range (minimum and maximum)

Include the age range for target population. If there is no maximum age, this can be noted, but a minimum age required for inclusion must be explicitly stated. If you have multiple research populations, clearly state the age range for each group.

21-70 years old inclusive

20. Inclusion/Exclusion Criteria

Describe the specific criteria that will be used to decide who will be included in and excluded from the research from the population of interested or potential subjects. Define technical terms in lay language, as applicable.

To be eligible to participate in the study, patients must meet the following inclusion criteria:

9. Provide written informed consent before the initiation of any study-specific procedures. See for informed consent requirements;

NOTE: Patients who are unable to independently provide informed consent will be ineligible to participate in this study.

10. Male or female, between the ages of 21 and 70 years, inclusive;

11. Meets the Diagnostic and Statistical Manual of Mental Disorders, 5th Edition, Text Revision (DSM-5-TR) criteria for MDD without psychotic symptoms, as confirmed by a trained rater using the modified Structured Clinical Interview (DIAMOND) for DSM-5,

12. MADRS total score ≥ 22 at Screening (Visit 1) and Baseline (Visit 2)

13. Endorse ≥ 1 physical or sexual assault prior to age 16 on the NSW.

Many studies refer to early life trauma as prior to age 18. Here we define early life assault as less than 16, rather than 18, in order to ensure a clearer separation between early life and adulthood. While another option might be to restrict even further (e.g., age of trauma < 10), for feasibility (e.g., facilitating recruitment) and generalizability (e.g., results extend to MDD and early life trauma more broadly than just early childhood trauma), we decided on physical or sexual assault prior to age 16.

Regarding the focus on physical or sexual assault, there are two main reasons. First, the definition of physical and sexual assault can more easily be operationalized through a behavioral description of an event (e.g., has anyone hit you with a fist, has anyone hit you with an object, etc), enabling more precise assessment and detection. Second, there is a robustly elevated risk for mood disorders following assaultive traumas relative to non-assaultive traumas. As such, there is greater clinical need to establish adjunctive treatments among those experiencing assaultive traumas.

14. Participants must have been treated with the same dose of antidepressant therapy for at least 6 weeks, with less than 50% improvement, and be committed to the same stable dosing regimen for the Screening period and for the entire study, at or above the minimally adequate dose in the ATRQ. Documentation of stable and ongoing ADT must be verified by documentation from the subject's psychiatrist, pharmacist, primary care physician or other qualified healthcare professional.

15. Female of childbearing potential and agrees to use at least an acceptable method of birth control (including but not limited to hormonal contraception, intrauterine device, vasectomized partner, bilateral tubal occlusion, condom with or without spermicide, cap with spermicide, diaphragm with spermicide, sponge with spermicide, or double barrier methods) from the time informed consent is provided through the end of the SFU period. **NOTE:** Females of non-childbearing potential (defined as either permanently sterilized, or post-menopausal females [defined as at least one year with no menses without an alternative medical explanation]) are exempt from the birth control requirement.

16. Ability to follow study instructions and likely to complete all required visits.

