The sponsor has requested expedited review in order to ensure funds are available for this project.

3. Is the research taking place at or using data from any of the following:

Knowing when UT's external clinical partners are involved helps inform IRB review and reporting.

- None of these
- Health Discovery Labs
- Central Health

- CommUnity Care
- Ascension locations → *Submit a request to the [Seton Site Approval Tool \(SAT\)](#) and upload the confirmation email that states the request has been submitted in UTRMS under "Other Documents." Please note, we do NOT need the final approval letter (you will not receive SAT approval until after IRB approval is granted). If you encounter issues or have questions about SAT, please reach out to [contact].*

4. Research Hypotheses

Please describe the research aims and hypotheses in the box below. Note: Procedures will be explained in a separate section below.

Aim 1: To assess the efficacy of lumateperone 42 mg administered once daily compared with placebo in the treatment of patients with Major Depressive Disorder and early life abuse, as measured by change from baseline to end of Week 6 in MADRS total score.

Aim 2: To assess neurocircuitry encoding of threat and reward learning as predictors of lumateperone response and as mechanisms of treatment action, and assess the change from pre-dose to post-dose of task-evoked brain activation.

Aim 3: MADRS response rate (proportion of subjects with an improvement $\geq 50\%$ in the Baseline MADRS total score) at Week 6 of Lumateperone as compared to Placebo.

Aim 4: MADRS remission rate (proportion of subjects with a MADRS total score ≤ 10) at Week 6 of Lumateperone as compared to Placebo.

Aim 5: To assess the efficacy of lumateperone 42 mg administered once daily compared with placebo in the treatment of patients with Major depressive Disorder and early life abuse, as measured by change from baseline to end of Week 6 in Clinical Global Impression-Severity (CGI-S) score.

5. Study Background

Provide the rationale and the scientific or scholarly background for the proposed activity, based on existing literature (or clinical knowledge). Describe the gaps in current knowledge that the project is intended to address.

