Screening Period - After signing the ICF, an identification number will be assigned to the subject. Prior to randomization, all subjects will enter a 2 week-day screening period (Screening) to determine eligibility. Eligible subjects must meet the Diagnostic and Statistical Manual of Mental Disorders, Fifth Edition (DSM-5) criteria for MDD without psychotic features, based on the DIAMOND (Diagnostic Interview for Anxiety, Mood, and Other Neuropsychiatric Disorders), with a current major depressive episode of at least 8 weeks in duration. They must have had an inadequate response (<50% symptom reduction) to an adequate trial of at least 1 antidepressant therapy (ADT) (as determined by administering the Massachusetts General Hospital Antidepressant Treatment History Questionnaire [ATRQ]) in their current Major Depressive Episode (MDE). During Screening Period (2 weeks) patient eligibility will be assessed and a Pre-dose fMRI performed.

Double-blind Treatment Period - Double-blind Treatment Period (6 weeks) during which all eligible patients will be randomized to receive lumateperone 42 mg or placebo in 1:1 ratio. At Baseline (Visit 2), patients who continue to meet all eligibility criteria will be randomized to either lumateperone or placebo.

Safety Follow-up Period in which all patients will return to the clinic for a safety follow-up visit approximately one week after the last dose of study treatment. All patients will complete a post dose MRI 1 week after the 6-week study period is completed.

- During the Pre-Dose and Post-dose MRI, Participants will undergo standard structural imaging as well as functional imaging during computational threat and reward learning tasks. Computational neuroimaging approaches will characterize neurocircuitry encoding of anticipating and delivery of threat and reward outcomes, enabling testing of predictors of lumateperone clinical response and mechanism of treatment action.

- Patients who discontinue study drug prior to Week 6 but agree to continue participation in the Double-blind Treatment Period (DBTP) should be seen at all subsequent protocol-defined visits up to week 6 and should also return for the SFU Visit for post dose MRI. Study drug will no longer be dispensed for these patients and the clinical management of these patients will be at the discretion of the Investigator.

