- *This is a “Multi-Site Study that involves more than one site performing ALL aspects of the research procedures as outlined above.” OR “This is a Collaborative Study that involves UT Austin researchers working with external researchers who are engaged in performing the following study activities (list activities).”*
- *For assistance with Multi-Site/Collaborative research, review [UT Guidance: Submitting Studies Relying on UT IRB](#), download HRP-UT932 Request to Rely Assessment Form from the [UTRMS-IRB Library](#) and email [contact].*

This is a single site, randomized, double-blind, placebo-controlled study to evaluate the efficacy of lumateperone as an adjunctive treatment of patients with MDD and a history of early childhood abuse. During the study subjects currently receiving approved dosing regimen of ADT, who experience an inadequate therapeutic response according to MADRS score at Baseline, will be randomized in a 1:1 ratio to Lumateperone 42mg or placebo, and receive treatment for 6 weeks. The primary efficacy analysis will be based on the week 6 assessment of the primary and secondary efficacy endpoints. The overall duration of the study, including Screening and intervention period, will be approximately 9 weeks per subject: a 2-week screening period, 6 weeks of double-blind treatment, and a 1-week safety follow-up visit.

The study design is presented in Figure 1.

Figure 1.

The study will be conducted as follows:

- Screening Period (2 weeks):
- A 2-week Screening Period during which patient eligibility will be assessed. After obtaining written informed consent, diagnostic interviews and physical examinations will be conducted, vital signs and ECGs will be assessed, and blood and urine samples will be collected for laboratory assessments. With the exception of stable, allowed concomitant medications, patients must discontinue prohibited psychotropic drugs during the Screening Period. The following rating scales will be administered.

Clinician Rater: CAPS-5, MADRS, DIAMOND, SCID-5 Borderline Personality module, CGI-S, MGH-ATRQ, CSSRS

PROS, GAD-7, QIDS-SR-16, EQ 5D-5L, CTQ, GASS, PCL-5, NWS, MCI

Once deemed eligible, the subject will also be offered to enroll in the optional EMA wellness app to be completed 3X daily from screening visit to the end of study visit

- Double-blind Treatment Period (DBTP, 6 weeks):

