4.2.3 Double-blind Treatment Visits (Visits 3-7 ;Weeks 2-6)

1. Record AEs as reported by patient or observed by Investigator
2. Review concomitant medications
3. Study drug compliance check, return unused Meds at each visit
4. Vital signs (BP, pulse rate, body temperature, respiratory rate) and weight
5. Assessment Scales: MADRS, CGI-S C-SSRS, HAMD-17, GAD-7, PHQ-9, QIDS-SR-16, EQ 5D-5L and GASS
6. Lab tests for Hematology for CBC will be completed at wee4 and week6 visits and Complete BW similar to screening visit will be completed at Week-7
7. EMA Wellness App (Optional)

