7.4 Efficacy Assessments

The Schedule of Assessments ([Table 1](#)) outlines the efficacy assessments to be performed throughout the study and their timing. For assessment scales performed at each visit, MADRS must be the first assessment performed by the rater at the site. Subsequent assessments, following MADRS, can be conducted in any order as determined by the investigator's discretion. The following order of assessments is recommended, from the least to the most invasive procedure: all assessment scales, vital signs, ECGs and lastly blood draw as indicated in [Table 1](#).

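### Table 1 schedules no CGI-S rating at Visit 7 (Week 6), the visit at which a confirmatory CGI-S endpoint is defined

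*Protocol*

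**What the plan says.** **Endpoint.** Aim 5 (item 4, Research Hypotheses) compares the arms "as measured by change from baseline to end of Week 6 in Clinical Global Impression-Severity (CGI-S) score". The secondary estimand paragraph numbered 10.2, under Section 11.3, states: "The key secondary efficacy endpoint is the change from baseline to end of Week 6 in the CGI-S score". Section 11.4 ranks the same variable third among three key secondary variables: "Change from Baseline to EOT Week -6 in the Clinical Global Impression of Severity (CGI-S) score, Lumateperone as compared to placebo". It limits confirmatory testing to the primary and these three, in hierarchical order.

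**Visit.** Section 11.4 ties Week 6 to Visit 7: "The primary estimand will be estimated as the difference between treatment means (MMRM least-squares) at the EOT Week 6 (Visit 7". Section 11.3 also gives Visit 7 for Week 6, and the Table 1 header agrees. Item 7 (Study Procedure Description) adds: "The primary efficacy analysis will be based on the week 6 assessment of the primary and secondary efficacy endpoints".

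**Schedule.** Section 7.4 says that Table 1 "outlines the efficacy assessments to be performed throughout the study and their timing". The CGI-S row of that table is filled at Visits 1, 2, 4, 6 and 8/ET and empty at Visits 3, 5 and 7.

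**Conflicting text.** Section 4.2.3, which covers Visits 3 to 7 (Weeks 2 to 6), gives this list: "Assessment Scales: MADRS, CGI-S C-SSRS, HAMD-17, GAD-7, PHQ-9, QIDS-SR-16, EQ 5D-5L and GASS". The Visit 8 list (Section 7.2.4) contains no CGI-S, although Table 1 marks it there.

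**The concern.** The visit that defines the endpoint is one at which the schedule table asks for no rating. A clinician's global rating that was not made at the visit cannot be recovered afterwards, so no later analysis decision can repair the loss. At stake is one of four confirmatory tests. The last on-treatment CGI-S would then be at Visit 6 (Week 5), and the next rating would come only at safety follow-up.

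A separate, smaller point sits in the same section. Section 11.4 assigns MMRM to every confirmatory estimand, although MADRS response and remission are proportions at Week 6, not change scores.

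**Working it through.** **1. Is the blank real, or a shifted column?** The rows of Table 1, read cell by cell:

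| Row | V1 | V2 | V3 | V4 | V5 | V6 | V7 | V8/ET |
|---|---|---|---|---|---|---|---|---|
| Study week | -2 | 1 | 2 | 3 | 4 | 5 | 6 | 7 |
| CGI-S | X | X | – | X | – | X | – | X |
| MADRS | X | X | X | X | X | X | X | X |
| Drug dispensing | – | X | X | X | X | X | – | – |
| fMRI | – | X | – | – | – | – | – | X |

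The full MADRS row fixes only the number of cells. The rows with gaps test the alignment. Dispensing at Visits 2 to 6 matches Section 3.1 (baseline, then weekly until Week 5). fMRI at Visits 2 and 8 matches item 7 (baseline and safety follow-up). The columns are aligned, and the Visit 7 CGI-S cell is empty.

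**2. Ratings available at Week 6** (50 patients, 25 per arm, no dropout assumed)

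- CGI-S under Table 1: 0 of 50.
- CGI-S under Section 4.2.3: up to 50 of 50.
- MADRS under Table 1: up to 50 of 50.

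**3. Can the planned model give a Week 6 contrast without Visit 7 ratings?** Section 11.4 specifies treatment, visit, treatment-by-visit, number of failed prior treatments and baseline. Section 11.2 plans similar models for secondary endpoints. With K visit levels the fixed-effect columns are

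1 (intercept) + 1 (treatment) + (K − 1) (visit) + (K − 1) (treatment-by-visit) + 1 (baseline) + 1 (prior failures) = 2K + 2.

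A Visit 7 level with no data leaves two columns at zero, the visit effect and its treatment interaction, so the rank drops by 2.

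| CGI-S ratings used | K, with a Visit 7 level | Rows | Columns | Rank | Visit 7 contrast |
|---|---|---|---|---|---|
| V4, V6 | 3 | 50 × 2 = 100 | 8 | 6 | not estimable |
| V4, V6, V8 | 4 | 50 × 3 = 150 | 10 | 8 | not estimable |
| V4, V6, V7 | 3 | 50 × 3 = 150 | 8 | 8 | estimable |

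Imputation does not help: neither arm would have an observed Visit 7 CGI-S value on which to fit an imputation model.

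**4. Can Visit 8 stand in for Visit 7?** Item 6 (Design and Methodology) describes a "safety follow-up visit approximately one week after the last dose of study treatment", that is, about 7 days. Section 11.2 treats MADRS assessments made more than 3 days after the last dose as off-treatment and sets them to missing. As 7 > 3, the same rule applied to CGI-S would remove the completers' Visit 8 rating.

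**5. Can the slope analysis stand in?** Section 11.2 extends it to CGI. It could run on Visits 2, 4 and 6 (Weeks 1, 3 and 5), but a Week 6 value would be extrapolated by 6 − 5 = 1 week beyond the last on-treatment rating.

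**The case against.** The strongest reply is that the rating is scheduled. Section 4.2.3 is a step-by-step instruction to the site and names CGI-S for Visits 3 to 7, and no sentence ranks Table 1 above it. This stands in part: the defect is a contradiction between two schedules, and it does not show that CGI-S will never be rated at Week 6. The figure of 0 of 50 is one end of a range. But Section 4.2.3 does not settle the conflict. Sections 4 and 7.4 both point to Table 1 for timing, and the CGI-S description (Section 7.4.2) names no visits. The Section 4.2.3 list also departs from the table elsewhere: it includes HAMD-17 and PHQ-9, which have no row in Table 1, and GASS without limit, which Table 1 marks only at Visits 3, 5, 7 and 8/ET.

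Two further objections are fair. The rank figures only express the empty cell in model terms; they are useful mainly to show that adding Visit 8 data does not help. And the 3-day rule is written for MADRS, so carrying it to CGI-S is an inference from the plan for similar secondary models.

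On weight, CGI-S is last in the testing order, and the primary and the two other key secondary variables rest on MADRS, which Table 1 marks at Visit 7. That limits the severity but does not remove the error.

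On the separate point, the details of a binary model may well be left to a SAP, which is not shown here. The protocol is not silent, however: it names MMRM for all confirmatory estimands.

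**Conclusion.** The concern holds. Table 1 omits CGI-S at the one visit where its confirmatory endpoint is defined, and Section 4.2.3 says otherwise. Depending on which text the site follows, Week 6 CGI-S is available for 0 or for up to 50 of 50 patients, before dropout. In the first case the Week 6 contrast is not estimable from observed data, and neither Visit 8 nor the slope analysis is a clean replacement. This rests on the table as extracted, with the alignment supported by the dispensing and fMRI rows, and on an MMRM for CGI-S of the form given for MADRS. It should be fixed, but the primary conclusion of the trial is not at risk. The assignment of MMRM to two proportions is a separate error of method in Section 11.4; the scheduling finding does not depend on it.

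**What to change.** 1. Mark CGI-S at Visit 7 (Week 6) in Table 1.
2. Align the CGI-S visits across Table 1, Section 4.2.3 and the Visit 8 list in Section 7.2.4, so that a single schedule holds.
3. Separately, in Section 11.4, restrict MMRM to the MADRS and CGI-S change scores and name a binary-outcome analysis for response and remission at Week 6. One option is logistic regression adjusted for baseline MADRS and number of failed prior treatments.

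The cost is one mark in the table for a brief clinician rating at a visit already held, an edit to the visit lists and one sentence in Section 11.4. No visits or patients are added.
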